#### **E. Aim 2: Focus Group Procedures**

Prescreening and consent. Participants will be recruited from OSU student organizations, flyers on campus, Reddit, other social media, or through word of mouth from participants who completed the study. The recruitment materials will include a study phone number and an OSU email address that will be set up for the study. Individuals who are interested in the study will be asked to take an online screener or, if they have questions, to call or email the study email address.

Individuals who are deemed eligible via the online screener will be asked to share their contact information. An IRB-approved study team member will contact eligible individuals to review informed consent. Eligible participants will complete a verbal informed consent. The research team member will read the informed consent script and verbally explain the online questionnaire and focus group process. The research team member will indicate that participation in the questionnaire and focus group is voluntary. The eligible participant will be given an opportunity to ask questions and have all questions answered to their satisfaction. Once the eligible participant understands the consent form and process, then and only then will the eligible participant be asked to give verbal consent. Eligible participants that do not consent will be released at this time. Consenting participants will be emailed the informed consent script for their records.

The research team member will ask eligible and consented participants for an email address for online questionnaire distribution and to send information for the future focus group. After the call has concluded, the research team member will email participants a link to a short questionnaire distributed via Qualtrics with questions about tobacco use, intentions to quit smoking, and demographic characteristics. A PDF copy of the informed consent will be available for download as part of the online baseline survey.

Focus group procedures. On the day of focus group, OSU IRB approved study personnel will provide an opportunity for verbal reconsent immediately preceding the focus group. Prior to audio-recording, the IRB-approved research team member will re-affirm participant consent. The research team member will indicate that participation in the focus group is voluntary and that participants may withdraw participation at any time. Eligible participants who do not reaffirm consent to focus group participation will be released at this time.

Focus groups will take place in-person or online via CarmenZoom in a secure, private space. A growing body of evidence describes the use of web-based videoconferencing platforms—also known as Voice over Internet Protocol (VoIP)-mediated technologies (e.g., CarmenZoom, Skype, FaceTime)—for collecting data in qualitative studies. Zoom, in particular, has been cited by qualitative interview participants as straightforward, easy to use, and preferred for its “robust but simple privacy and security options” (e.g., secure webinar options and local device- or server-based recording). Online focus group are also a feasible option for conducting qualitative human subjects research with national samples.

All focus groups will be audio-recorded and transcribed for subsequent analysis. Focus group length is anticipated to be about 60-90 minutes. Audio-recorded data will capture participant' responses to questions about nicotine and tobacco use, public education messages about nicotine and tobacco, and textual and visual elements of LGBT cultural targeting.

**Sources of Materials:** Information from focus groups (conducted via CarmenZoom) will be obtained in this study to pre-test culturally targeted anti-polytobacco messages. Focus groups will either be conducted in-person and audio-recorded or will be conducted remotely using CarmenZoom

(<https://resourcecenter.odee.osu.edu/carmenzoom>), an enterprise-wide web conferencing tool that allows individuals to connect via videoconference or telephone.

- For in-person focus groups we will use a digital audio recorder. Post focus group, audio data will be immediately downloaded and transferred to One Drive for secure long-term storage. Only the focus group identification number will be used to identify the data source.
- For remote focus groups, researchers will use CarmenZoom's videoconferencing platform to enable CarmenZoom's secure audio-recording feature. Participants will be asked to call into the meetings via telephone only. CarmenZoom stores audio-recorded sessions and protects sensitive data using real-time encryption of meetings and automatic cloud-based recording and storage to the OSU Carmen Zoom online remote server networks (i.e., "the cloud") for 180 days. These recordings will be downloaded and transferred to Microsoft Teams/One Drive for secure long-term storage. Only the focus group identification number will be used to identify the data source.

Participants will receive \$30 via Amazon gift card distributed via email in appreciation of their time.  
Aim 2 focus group data will be used to further develop/refine text and graphics for anti-tobacco messages that will be further tested in the Aim 2 eye-tracking study.

#### **F. Aim 2: Virtual Eye-Tracking Experiment (NCT05972941) Procedures**

Prescreening, consent, and study procedures:

Participants will complete an online screener via RedCap after viewing a social media ad or flyer, receiving an email from participating in another study, or via word-of-mouth from other participants. Eligibility screeners will include 'nedCAPTCHA', a module that provides the use of a classic image CAPTCHA with distorted text, a math problem, or a custom question/answer challenge. These CAPTCHAs are similar to the 'I am not a robot' button or the 'Click all of the traffic lights' CAPTCHAs often seen in online forms. nedCAPTCHA is highly recommended by OSU OCIO for projects using the Public Survey Link option in REDCap. The module will help prevent bots from completing surveys. Eligible participants will be asked to report an email address and telephone number for future contact if enrolled into the study.

As the eye-tracking component of this survey requires that participants complete the survey on a laptop or desktop with a webcam, we will include a question at the end of the eligibility screener asking participants if they are currently participating on a desktop/laptop with webcam. If participants meet all other eligibility criteria, but they are taking the screener on a device other than a laptop or desktop with webcam (e.g., a tablet or smart phone), they will be directed to the following opt-in statement: "I have a desktop computer or laptop but I am currently on my phone or tablet. Please email me a link to the consent form and I will complete the iMotions task on my laptop/desktop." Research study staff will then contact eligible and interested participants via email, phone call or text to complete the informed consent and participate in the online eye-tracking experiment. After reviewing the consent form, participants will be asked to electronically indicate their consent to participate. Online consent will be documented in REDCap.

If eligible participants indicate that they are currently taking the eligibility screener on a laptop or desktop with webcam, they will be immediately directed to an informed consent describing the study purpose and detail

about the survey and the embedded remote eye-tracking experiment. After reviewing the consent form, participants will be asked to electronically indicate their consent to participate. Online consent will be documented in REDCap.

Consented participants will be directed to the online survey. At the beginning of the survey, we will ask participants to confirm that they are taking the survey in a well-lit area and that their face and eyes are clearly viewable on their webcam. We will include example images of good vs. poor lighting. If participants respond, "I am using a desktop computer or laptop. I am in an area that is well lit, and I can see my face and eyes clearly," then they will be directed to the survey. If they respond, "I have a desktop computer or laptop, but I am currently in an area that is not well lit and I cannot see my face or eyes clearly on my webcam. Please email me a link to the survey, and I will complete the iMotions task when I am in an area with better lighting," then research staff will then email these participants a direct link to the survey that they can take at a convenient time. We will send up to 9 survey reminders via email, phone call or text.

Once the survey begins, participants will complete baseline questionnaires before proceeding to the remote eye-tracking experiment. At this point, participants will be randomly assigned to 1 of 2 experimental conditions (CT or NT messages). iMotions provides an online platform for remote eye-tracking data collection using a webcam connected to a desktop or laptop computer to track eye movements during the study. Participants will be informed that their webcam needs to be turned on during the study. Prior to viewing images, calibration procedures will be conducted to assure data quality; if participants cannot be calibrated, participation will end. Participants will view a series of randomized messages (8 messages, for 10 seconds each, within assigned conditions. A 10 second viewing time is greater than needed (6 seconds) to assess visual attention.

Message versions will include similar messaging and imagery but different layouts to mitigate viewing bias, as we anticipate that a majority of participants will tend to read left to right and top to bottom. After each message, participants will report perceived effectiveness and reactance. To re-center eyes, participants will view an "X" centered on-screen for 10 seconds. Post eye-tracking, participants will complete demographic and contextual questions prior to exiting the survey. Participation is expected to last 20 minutes. Participants will receive a \$50 gift card.

We will contact participants 1-week post-experiment via a RedCap survey to assess message recall, recent nicotine and tobacco use, and risk perceptions. Participation is expected to take 10-15 minutes, for which they will receive a \$20 gift card.

Participants may be recontacted to resolve discrepant data entries. We will recontact participants via the study email address or phone to resolve the problem. If we are unable to resolve the discrepancy, we are unable to provide a study incentive.

Participants will also be asked if they would be willing to be contacted to participate in future studies. Depending on their preferred contact method (e.g., email or phone), we will keep a list of those who say “yes” to being contacted for future studies saved in REDCap.

All research-related data will be saved on a password protected computer on The Ohio State University server. Upon completion of data collection, all data will be de-identified and stored on The Ohio State University Microsoft Teams/OneDrive.

Participants who have consented to version 1 of the consent form will be asked to consent to version 2 which specifically outlines details related to facial recording. Participants will be sent an individual email using the secure databasing platform, REDCap and will be given the option to consent or decline study participation electronically within REDCap. We will recontact participants up to 9 times to seek reconsent.

At the end of data analysis, participants will be emailed once their face recording data has been deleted.

### ***Sources of Materials***

Information from an online survey with embedded remote eye-tracking will be obtained in this study to experimentally test the effect of exposure to anti-polytobacco messages with and without cultural targeting on message effectiveness and reactance, and tobacco harm perceptions. Data from the pre- and post-eye-tracking surveys will be collected in Qualtrics. Data from the embedded remote eye-tracking study will be collected via iMotions, a secure, online data collection platform. No self-report or eye-tracking data collected are directly linked to participant identifying information: self-report and eye-tracking data collected through iMotions are tracked using a unique, numeric participant identifier. Remote eye tracking is performed through the respondent's own webcam and allows for recording and analysis of responses to images tracking visual attention. Webcam recordings of facial data will be recorded and stored within the I-motions software. Post-participation, the data will be downloaded. Facial recording data will be reviewed by staff members for compliance-related purposes only, and will not be used for analysis. All survey and eye-tracking data will be stored on The Ohio State University Microsoft Teams/OneDrive. Data collected in follow-up surveys will be collected and stored in RedCap and linked to the participant's personal identifier. At the conclusion of the study, all facial recognition data will be deleted.

## **V. RISKS, BENEFITS, SAFETY PLANS**

### **A. Risks associated with the study**

Potential risks are minimal for the focus group and survey studies. Some of the questions may upset individuals; however, we have used these questions and procedures in many previous studies without upsetting participants. A potential risk is loss of confidentiality. In our screener, we collect participant contact information. Also, iMotions eye-tracking software saves facial data to track eye movements; however, this information will only be used to track participant compliance to study procedures, will not be used during data analysis, and will be deleted upon study completion. We will not use facial recording information for any other purpose, and because all study data including facial recording is stored on a secure password-protected University-sponsored laptop, we do not believe this represents an increase in risk for study participants. Participant privacy is protected because participants will consent to research before any study activities are performed. Because facial recordings are collected, participants are informed of this at several points throughout the study

and will be given the option to discontinue participation at any time. For Aim II Eye Tracking Study, we are collecting facial recordings because it is a requirement of the software. We are only using facial recordings for compliance purposes. We also collect first and last name, email address, zip code, county, and sexual orientation from participants, which may be sensitive. Participants provide this by self-report and may skip any question that is uncomfortable. We have rigid procedures in place to protect against loss of confidentiality. Participant identifiers will be kept in password-protected files, stored on secure OSU servers.

## **B. Benefits associated with the study**

There are no direct benefits to be gained by participants. However, the anticipated societal benefit resulting from this study is considerable, given the increasing prevalence of polytobacco use, including ENDS. Societal benefits include increased public health resulting from this study providing evidence that directly informs and strengthens FDAs tobacco public education efforts. Few studies have been conducted on effectively communicating tobacco risk to polytobacco users and at the same time, there is mounting evidence that LGBT young adult polytobacco users, a vulnerable population from a tobacco control perspective, are largely misinformed of the risks of combustible tobacco and ENDS use.

## **VI. DATA ANALYSIS**

### **A. Aim 1, Phase 1: Study 1—FOCUS GROUPS Data Analysis**

For focus groups, the goal is to refine messages and determine which images should be matched to the AR and RR anti-tobacco messages. These images will then move on to Aim 1 Phase 2 of this study. We will qualitatively summarize the feedback in response to each focus group question.

Sample size justification: For Aim 1 Phase 1: Study 1—FOCUS GROUPS: A planned analytic sample size of  $N = 24$  participants is standard for usability research, where the aim is to test existing messages to improve any communication issues. If we do not reach thematic saturation during the first round of focus group, we will enroll up to an additional 24 participants (for a maximum analytic of  $N = 48$ ). The sample size was inflated to 29 participants for each round of focus groups to allow for 20% dropout; resulting in a maximum overall sample size of  $N = 58$  focus group participants.

### **B. Aim 1, Phase 1: Study 2-ONLINE RATING SURVEY Data Analysis**

For online rating survey data, we will describe mean and median values of participants' ratings of perceived message effectiveness, likeability, and reactance.

In exploratory analyses, we will assess whether there are systematic differences in participants' ratings by message type (AR vs RR), gender, LGBT status (vs non-LGBT), race/ethnicity, age (e.g., 18-24 vs 25-35) and tobacco user type (e.g., current, former, never polytobacco user). We will test mean differences between groups using t-tests or ANOVA. If there are violations of assumptions (e.g., normality) we will test median differences between groups using Wilcoxon rank-sum test (two groups) or Kruskal Wallis test (more than 2 groups).

We will also run exploratory regression models to evaluate the effect of risk message type (e.g., absolute risk vs. relative risk) and efficacy message type (e.g., quit; switch; combination) on messages on perceived message effectiveness, likeability, and reactance; controlling for pro- and anti-tobacco marketing exposure, baseline risk and efficacy perceptions and behavioral intentions. For models testing the effect of efficacy

messages, we will conduct overall F-tests to determine if there is an effect of efficacy message type in each model. If so, pairwise t-tests will be conducted, and Holm's procedure will be used to control Type I error rate.

Sample Size Justification: For Aim 1, Phase 1, Study 2—ONLINE RATING SURVEY: An analytic sample size of 200 participants per group will allow us to detect differences between two groups in terms of perceived message effectiveness. Assuming a pooled standard deviation of 1.0 units, the study would require a minimum sample size of  $n = 199$  for each group to achieve power of 80% and two-sided significance level of  $p = .05$  for detecting a 0.25 unit difference in perceived message effectiveness scores, which has been reported previously in the literature. Under these same parameters, we will be able to detect a 0.25 unit difference in PME scores with 75% probability assuming a significance level of  $p = 0.1$ . As multi-group comparisons are exploratory, we believe this a prior sample size calculation is appropriate. As our desired analytic sample size is  $N = 500$  participants ( $n = 250$  participants per experimental group; AR vs RR messages); we have inflated our overall sample size is inflated by 10% to account for estimated inconsistencies between prescreening and survey responses, resulting in an overall sample size of  $N = 550$ .

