**Table 2. Message sets for formative message testing in a 2x3 between subjects experiment (Aim 1 Phase 2)**

		THREAT	
		ABSOLUTE RISK (AR)	RELATIVE RISK (RR)
EFFICACY	Quit only (Q)	Set 1: AR/Q (n = 8)	Set 2: RR/Q (n = 8)
	Switch only (S)	Set 3: AR/S (n = 8)	Set 4: RR/S (n = 8)
	Combined quit + switch (QS)	Set 4: AR/QS (n = 8)	Set 6: RR/QS (n = 8)

**Aim 1, Phase 1: Study 2 –ONLINE RATING SURVEY:** In Phase 1, Study 2 we will conduct an online survey to quantitatively examine young adults’ perceptions of 8 absolute risk and 8 relative risk anti-tobacco messages and quit/switch efficacy statements. To reduce participant burden, each participant will view a random sample of messages as follows: n = 5 absolute and relative risk anti-tobacco messages (of N = 24), and n = 3 (of N = 12) efficacy messages. They will be asked to rate absolute and relative risk antitobacco messages and quit/switch efficacy statements for perceived message effectiveness, likeability, and reactance.

**Aim 1, Phase 1: Study 3 –IN-DEPTH INTERVIEWS:** Interviewees will be asked to share their reactions to the 24 textual anti-tobacco messages tested in Study 2. Specifically, interviewees will be asked to rate their top 5 (of N =12) absolute risk and top 5 (of N =12) relative risk antitobacco messages. We will then qualitatively explore their rationale for their top 5 selected messages.

**Aim 1, Phase 2: ONLINE FACTORIAL EXPERIMENT** (NCT05393869): Using a 2x3 factorial experiment (Table 2), plus control group design we will test the influence of AR and RR message framing on perceived effectiveness, tobacco risk perceptions, and behavioral intentions in young adult ever polytobacco users. Participants will be randomized to one of 8 conditions, including 6 experimental sets of AR and RR anti-tobacco messages (Table 3) and a control set of AR or RR regulatory control messages. We will present 8 messages within each experimental and control set. An expert panel of scientists, selected and invited by the mentoring team, will review all messages, which we will further refine based on expert feedback prior to testing in Aim 1, Phase 2 (NCT05393869).

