## **C. AIM 2 Study (NCT05972941) Procedures (R00 Grant Year 1) Overview**

- Our Aim 2 goal is to identify if culturally targeted (CT) or non-targeted (NT) anti-polytobacco messages are most effective for engaging LGBT YA. Using the most effective NT messages from Aim 1 (12 RR; 12 AR), we will create a set of CT messages. Message framing will remain consistent between CT and NT messages; however, CT messages will include graphics representing LGBT values per the PI's formative research and extant literature. Focus groups with LGBT tobacco users will be used to elicit recommendations for refining CT messages, which we will change accordingly. Then, an expert panel of scientists and LGBT community members will review CT messages prior to testing as part of our Community Advisory Board for this study and beyond. In the Aim 2 clinical trial (NCT05972941), a virtual eye-tracking study, participants will be randomized to view CT or NT messages in our virtual lab where we will assess eye-tracking, self-reported perceived effectiveness, risk perceptions, and behavioral intentions. We aim to determine the effects of cultural targeting on attention to anti-polytobacco messages and perceived effectiveness among LGBT young adult polytobacco users. The most effective messages (CT or NT) will be tested in Aim 3 for their influence on risk perceptions and tobacco use.
- **Aim 2 Focus groups:** Focus groups will take place in-person or online via CarmenZoom in a secure, private space. Eligible participants will complete a verbal informed consent and online baseline survey. A PDF of the informed consent will be made available for download as part of the online baseline survey. Consent will be reaffirmed prior to commencing discussions and audio-recording. Participants will receive \$30 for their time.
- **Aim 2 Eye-tracking experiment (NCT05972941):** The eye-tracking experiment will take place virtually using iMotions, an online platform for remote eye-tracking data collection, and Qualtrics survey software. Eligible participants will complete written informed consent via RedCap. A PDF of the informed consent will be made available to participants for download. Participants will receive \$50 for the eye-tracking survey. Participants will be contacted one-week after participating for a follow-up survey to assess recall. Participants will receive \$20 for participating in the follow-up survey.

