#### **B. Aim 1, Phase 1: Study 2—ONLINE RATING SURVEY Procedures**

**Prescreening and consent.** Participants will be recruited via Prolific, an online platform open to participants who are compensated for completing surveys and online behavioral experiments. Prolific is an efficient online recruitment platform, ideal for pilot studies, as it can deliver a high number of participants, per day, at low cost (recommended, minimum \$0.175 per minute of survey participation time). Data quality provided by Prolific

samples is high and comparable to that from traditional college student samples. Prolific offers access to over 38,000 United States nationals. Prolific samples are young; approximately 1/3 of the Prolific population reports ages < 35 years old, which makes Prolific an ideal pool for recruiting young adult survey participants. Prolific is also a viable method for recruiting hard-to-reach populations for survey research, including LGBT populations.

Prescreening will be conducted via Prolific. Prolific is able to segment our population of interest for age (18-35 years) and currently residing the United States. It can also help us track gender and sexual orientation in order to balance recruitment. We are able to add in a custom pre-screening question to assess for prior history of ever nicotine or tobacco use (i.e., use of combustible tobacco or e-cigarette products at least once).

Participants who meet eligibility criteria will be directed to an online survey administered via Qualtrics. Consent will be completed online prior to the Qualtrics survey.

Qualtrics survey procedures. Following online consent, participants will be directed to complete a survey that includes questions assessing tobacco use, including exposure to tobacco related advertising, coupons, and discounts; harms perceptions and tobacco-related behavioral intentions (i.e., quit, switch). It is estimated that the survey will take 20 minutes to complete.

Participants will answer baseline survey questions before viewing a random sample of 5 messages (of N = 24); they will rate each message for perceived effectiveness, likeability, and reactance. After viewing all messages, participants will complete a post-survey and receive \$0.175/minute (estimated \$3.50) via Prolific for participating.

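### Study 2 message scores are raw means and medians from a 5-of-24 random draw; adding a participant effect would cut avoidable between-rater noise at no cost in data

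*Combined protocol and SAP*

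**What the plan says.** The Study 2 paragraph under Table 2 (section III.B) gives every rater a randomly drawn subset, of this size: "n = 5 absolute and relative risk anti-tobacco messages (of N = 24), and n = 3 (of N = 12) efficacy messages". Section IV.B repeats the 5 of 24 and has each message rated separately for perceived effectiveness, likeability and reactance.

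Section VI.B gives the lead analysis: "we will describe mean and median values of participants' ratings of perceived message effectiveness, likeability, and reactance". The exploratory tests and regressions that follow compare message types and participant subgroups, the regressions "controlling for pro- and anti-tobacco marketing exposure, baseline risk and efficacy perceptions and behavioral intentions". No analysis estimates individual messages with a participant term, and none refers to several ratings coming from one person.

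The sample-size text in VI.B sets an analytic sample of 500 and assumes an SD of 1.0. It describes the 500 as 250 participants per group, AR versus RR, which does not fit a single draw from all 24 messages.

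**The concern.** Any two messages are scored by largely different people. Some people rate everything generously and others harshly, so the raw difference between two message means mixes a difference in message quality with a chance difference between the people who drew each message. Each person rates several messages, however, so part of that variation can be estimated and taken out. Raw means and medians do not use this information.

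The stake is the precision of message-level comparisons. Study 2 and the interviews work with 12 AR and 12 RR texts, while Phase 2 shows 8 messages per set, so some narrowing has to happen. If Study 2 scores inform it, avoidable noise makes the choice somewhat less reliable.

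**Working it through.** **The plan's own figure.** The only Study 2 calculation is 199 per group for a 0.25-unit difference, SD 1.0, 80% power, two-sided 0.05. It compares two groups and does not address individual messages. It does not reproduce: 2 × (1.960 + 0.842)² / 0.25² gives 252 per group. A one-sided 0.05 or two-sided 0.10 level gives 2 × (1.645 + 0.842)² / 0.25² = 198 (199 with the t distribution). That is a separate matter. Only the SD of 1.0 and the analytic N of 500 are carried forward here.

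**Inputs.** From the documents: N = 500 raters, k = 5 messages each, v = 24 messages. Assumed: the rater share of variance ρ, varied from 0.1 to 0.7.

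**Design quantities** (treated as balanced, which random draws approximate):
- Raters per message: r = Nk/v = 500 × 5/24 = 104.2. For efficacy statements: 500 × 3/12 = 125.
- Raters shared by a pair of messages: λ = r(k − 1)/(v − 1) = 104.2 × 4/23 = 18.1.
- Efficiency factor: E = v(k − 1)/[k(v − 1)] = 96/115 = 0.835.

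**Variance of a difference between two messages:**
- Raw means: (2/r)(1 − ρλ/r)
- Random participant intercept: 2 / {r[E/(1 − ρ) + (1 − E)/(1 − ρ + kρ)]}
- Fixed participant effects: 2(1 − ρ)/(rE)

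Example at ρ = 0.5:
- Raw: 0.0192 × (1 − 0.087) = 0.0175, SE 0.132.
- Random intercept: 2/[104.2 × (1.670 + 0.055)] = 0.0111, SE 0.106.

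| ρ | SE raw | SE random intercept | Reduction | SE fixed effects |
|---|---|---|---|---|
| 0.1 | 0.137 | 0.136 | 1% | 0.144 |
| 0.3 | 0.135 | 0.123 | 9% | 0.127 |
| 0.5 | 0.132 | 0.106 | 20% | 0.107 |
| 0.7 | 0.130 | 0.082 | 37% | 0.083 |

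Fixed participant effects do worse than raw means when ρ is below about 0.19. The random intercept does not. In simulation with the rater variance estimated from the data, the variance of a difference fell from 0.0179 to 0.0148, 0.0176 to 0.0112 and 0.0167 to 0.0069 at ρ = 0.3, 0.5 and 0.7. At 0.1 there was no loss (0.0189 against 0.0185).

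**Efficacy statements** (3 of 12): E = 24/33 = 0.727, and the reductions are about 1%, 6.5%, 17% and 33% at ρ = 0.1, 0.3, 0.5 and 0.7.

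**If raters are split by type** (250 per group, 5 of 12): r is still 104.2 and E = 48/55 = 0.873. The within-type reductions are 7%, 17% and 33% at ρ = 0.3, 0.5 and 0.7. The AR versus RR comparison gains nothing: its simulated SD was 0.066 by either method at ρ = 0.5 and a message SD of 0.1.

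**Effect on selection, if eight of 12 per type were chosen on score** (an assumption; one draw from 24, true message SD 0.15):

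| ρ | True best eight found, raw | Adjusted |
|---|---|---|
| 0.1 | 6.94 | 6.94 |
| 0.3 | 6.97 | 7.03 |
| 0.5 | 6.95 | 7.11 |
| 0.7 | 6.98 | 7.27 |

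For message SDs of 0.1 and 0.2 the gains were similar. The largest was 0.36 (6.67 to 7.03, at ρ = 0.7 and message SD 0.1). At SD 0.15, the average true quality of the chosen eight rises by 0.002, 0.003 and 0.006 rating SD at ρ = 0.3, 0.5 and 0.7.

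**The case against.** The other side has a good deal of weight. A reader might infer four things that the documents do not support.

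- **That the scores are biased.** Messages are drawn at random, so raw means are unbiased. Leniency adds sampling noise and no systematic distortion. Nor would a random intercept eliminate it; it reduces it by an amount that depends on ρ.
- **That the plan ranks messages on these means.** VI.B says only that ratings will be described. It does not say per message, and no section gives a rule by which Study 2 scores pick the Phase 2 messages. Focus-group feedback, interviews and expert review are the routes described for refining them.
- **That Study 2 alone compares messages within Phase 1.** In the Study 3 interviews, participants choose a top 5 of 12 for each type after seeing all 24. The sample is small (8 to 16), but the comparison is within person and free of this problem.
- **That the noise passes into Aim 2.** The Aim 2 overview says "Using the most effective NT messages from Aim 1 (12 RR; 12 AR), we will create a set of CT messages". Twelve and twelve equals the whole Study 2 pool in number, so no Study 2 ranking is implied. Phase 2 also has each participant rate all 8 messages in the assigned set, with about 400 participants per condition, and leniency cancels within a set.

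The practical gain is also small beside the 0.25-unit difference used in the sample-size text, and close to nil if ρ is near 0.1. All of this stands, and it limits the point to one of efficiency. It does not remove it: the raw mean remains a less precise message score than one available from the same data.

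**Conclusion.** The point holds as an optional improvement in precision. VI.B plans raw means and medians for ratings from an incomplete random draw and names no participant effect. A random participant intercept lowers the standard error of a message difference by about 1% to 37% for a rater share of variance between 0.1 and 0.7, and for selection it yields about 0.1 to 0.3 more of the true best eight of 12 at shares of 0.3 to 0.7. These sizes rest on an assumed rater share and message SD, neither of which the documents give, and on the one-draw-from-24 design. Under separate AR and RR groups the gain is somewhat smaller within type and absent for AR versus RR. No stated hypothesis test or conclusion is wrong because of this.

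**What to change.** In VI.B, for each of perceived effectiveness, likeability and reactance, fit a linear mixed model with message as a fixed effect and participant as a random intercept, separately for the risk messages and the efficacy statements. Report adjusted message means with standard errors, use them wherever individual messages are compared or chosen, and keep raw means and medians as a supplement. If the scores inform which messages go forward, say how.

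Reconcile the Study 2 paragraph in III.B (one draw from 24) with the sample-size text in VI.B (250 per AR or RR group), since this decides which comparisons benefit.

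The cost is a few lines of analysis text and one standard model per outcome and message type, with no change to the survey or sample. The Phase 2 sample section already reports a Phase 1 inconsistency rate, so Study 2 data may exist. The model can still be run on them, though possibly too late to affect which messages entered Phase 2.
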